Study Protocol and Statistical Analysis Plan

Isoflurane Sedation Using AnaConDa® Device with Non-Invasive Ventilation for Acute Exacerbation of COPD

**Protocol version 2.0
Dated 04.12.2022**

1. Protocol Synopsis

Title	Isoflurane Sedation Using AnaConDa® Device with Non-Invasive Ventilation for Acute Exacerbation of COPD
Study Design	Prospective, single-arm, interventional pilot study
Study Population	Adult patients (≥ 18 years) with acute exacerbation of COPD requiring NIV
Sample Size	20 patients (interim analysis after 10 enrollees; final analysis planned on 20)
Intervention	Isoflurane sedation via AnaConDa® device during NIV
Primary Objective	Incidence of intervention failure (intubation or excessive sedation)
Secondary Objectives	Safety (vitals, ABG changes), sedation depth (RASS), patient comfort (VAS)
Duration	24 hours of sedation monitoring; follow-up until discharge or intubation
Ethics Approval	BREC 23/121 (20.03.2023), in accordance with ICH-GCP and Declaration of Helsinki

2. Background and Rationale

Acute exacerbations of COPD (AE-COPD) frequently lead to hypercapnic respiratory failure, where non-invasive ventilation (NIV) reduces intubation and mortality risks. However, NIV intolerance due to agitation or dyssynchrony often necessitates invasive ventilation, with attendant complications. Volatile anesthetics like isoflurane, delivered via AnaConDa®, offer rapid, titratable sedation with bronchodilatory effects and minimal accumulation. Preliminary ICU studies suggest improved hemodynamics and faster recovery with inhalational sedation, but data in the NIV setting are lacking. This pilot protocol aims to assess feasibility and safety of isoflurane sedation via AnaConDa® in AE-COPD on NIV.

3. Objectives

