3.1 Primary Objective

- Evaluate the incidence of intervention failure, defined as either requirement for endotracheal intubation or occurrence of excessive sedation (RASS ≤ -3).

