9.1 Sample Size Justification

Assuming baseline NIV failure/intubation rate of 50%, a 30% absolute reduction requires 20 patients for 80% power at $\alpha=0.05$ (two-sided). Interim analysis after 10 patients will assess safety and futility.

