9.6 Interim Analysis

- After 10 patients, DSMC reviews safety: if > 50% failure or SAE rate > 20%, consider early termination.

10. Data Management and Quality Assurance

- Case report forms (CRFs) will capture all assessments.
- Data entry into secure electronic database with audit trail.
- Regular monitoring visits by Clinical Research Associate (CRA).
- Query resolution within 72 hours.

11. Ethics and Informed Consent

- Approval by Institutional Ethics Committee.
- Conducted per ICH-GCP and Declaration of Helsinki.
- Written informed consent obtained prior to any study procedure.
- Confidentiality maintained; data anonymized.

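### The only stated follow-up period ends at intubation, so deaths and serious events after intubation go unrecorded if SAE collection follows it

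*Combined protocol and SAP*

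**What the plan says.** The Duration row of the synopsis (section 1) reads "24 hours of sedation monitoring; follow-up until discharge or intubation". No other section gives a follow-up period. The assessment table in section 7 stops at 24 hours. Section 8 asks for SAEs to reach the DSMC within 24 hours, but it neither defines an SAE nor says from when until when SAEs are collected. Mortality and outcomes after intubation appear nowhere among the objectives or analyses.

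The background (section 2) names safety as an aim of the pilot, alongside feasibility. The SAE rate also has a role at the interim look after 10 patients, where section 9.6 says "if > 50% failure or SAE rate > 20%, consider early termination".

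Intubation itself is recorded. The primary endpoint in section 3.1 is failure "defined as either requirement for endotracheal intubation or occurrence of excessive sedation (RASS ≤ -3", and section 9.4 analyses time to intubation.

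**The concern.** The length of observation depends on the outcome. A patient who does well is watched to discharge; a patient who is intubated is watched only until the tube goes in. Death, aspiration, shock or prolonged ventilation after that moment falls outside the stated period. A patient who dies on the ventilator and one who is extubated quickly without complication would appear in the data as the same single failure.

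The background already says that NIV intolerance "often necessitates invasive ventilation, with attendant complications". That sentence is about invasive ventilation in general and is not evidence of harm from isoflurane, but it does show that the plan expects this period to carry risk. At stake are the completeness of the safety record in a first pilot of this sedation during NIV, and the SAE figure that the DSMC sees after 10 patients.

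**Working it through.** **1. The plan's own figure.** Section 9.1 starts from "Assuming baseline NIV failure/intubation rate of 50" percent and states that "a 30% absolute reduction requires 20 patients for 80% power at $\alpha=0.05$ (two-sided"). Tested as a single proportion against a fixed 50%, with 20% as the alternative:

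n = [(1.96 × √(0.5 × 0.5) + 0.842 × √(0.2 × 0.8)) / 0.30]² = [(0.980 + 0.337) / 0.30]² ≈ 19.26, rounded up to 20.

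An exact binomial check at n = 20, rejecting at 5 or fewer failures, gives a one-tail error of 0.0207 and power of 0.804. The stated 20 reproduces, and the end of follow-up does not enter it.

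**2. What truncation cannot change.** An intubated patient is already a failure. The primary proportion, the interim failure limit (above 50% of 10, so at least 6) and time to intubation are the same whether observation stops at intubation or continues.

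**3. How many patients could leave follow-up this way.** The documents give no pure intubation rate. The 50% in section 9.1 is a combined failure/intubation rate, and 50% − 30% = 20% is the hoped-for rate on the same scale. Treating every failure as an intubation gives an upper figure at each rate:

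- First 10 patients: 10 × 0.20 = 2 to 10 × 0.50 = 5.
- All 20 patients: 20 × 0.20 = 4 to 20 × 0.50 = 10.

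Some failures may be excessive sedation without intubation, and those patients stay in follow-up. These are counts of patients leaving observation, not of SAEs lost.

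**4. The SAE limit.** Above 20% of 10 means more than 2, so at least 3 patients.

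**5. Illustration under assumed rates.** The documents give no SAE rates, so these are assumptions: b = share of patients with an SAE before intubation or discharge (5–15%); π = share intubated (20–50%); q = share of intubated patients with a later SAE (20–60%); b and later events independent; intubation not itself an SAE; rate counted per patient. With truncation the rate is b. With full follow-up it is 1 − (1 − b)(1 − πq). The last two columns are the binomial probability of 3 or more in 10.

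| b / π / q | Rate, truncated | Rate, full | Patients with SAE of 20, truncated vs full | Limit reached, truncated | Limit reached, full |
|---|---|---|---|---|---|
| 5% / 20% / 20% | 5% | 1 − 0.95 × 0.96 = 8.8% | 1.0 vs 1.8 | 1% | 5% |
| 10% / 50% / 40% | 10% | 1 − 0.90 × 0.80 = 28% | 2.0 vs 5.6 | 7% | 56% |
| 15% / 50% / 60% | 15% | 1 − 0.85 × 0.70 = 40.5% | 3.0 vs 8.1 | 18% | 84% |

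The direction is the same in every row. The size depends almost wholly on inputs that the plan does not supply.

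**6. If intubation counts as an SAE.** Every intubated patient is then already counted, and the per-patient rate is 1 − (1 − b)(1 − π) with or without truncation. For b = 10% and π = 50% it is 1 − 0.90 × 0.50 = 55% either way. Only the number and type of later events, including deaths, are lost.

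**The case against.** The strongest reply is that no section ties SAE collection to the Duration row. Section 8 sets a reporting deadline with no end date, and the Duration row could be read as the window for failure and time to intubation only. That stands as far as it goes: the undercount is conditional. But the plan states no other period, so a site following it as written could reasonably stop at intubation.

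A second reply is that intubation may itself be an SAE, leaving the per-patient rate unchanged. The plan does not say. That reading sits awkwardly with section 9.6: with intubation at 20% and no other SAE, the chance of 3 or more in 10 is 32%, and at 50% it is 95%, so the SAE limit would often be reached even at the hoped-for rate. This is an argument about intent, not proof. Deaths after intubation are lost on either reading.

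A reader might also infer more than the documents support:

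- *That follow-up closes on exactly the patients harmed by isoflurane.* It does not. Patients with excessive sedation, hypotension, bradycardia or respiratory depression who are not intubated stay in follow-up to discharge.
- *That the safety conclusion as a whole is biased.* Intubation enters the primary endpoint and the failure limit, and the listed safety measures include vital signs and blood gases to 24 hours. Truncation bears on the SAE count and on later outcomes.
- *That longer follow-up would show whether sedation delayed intubation or worsened its result.* This is a "Prospective, single-arm, interventional pilot study" with no concurrent control, so later data would describe outcomes but not attribute them.
- *That missed events decide whether the trial stops.* Section 9.6 asks the DSMC only to consider termination.

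**Conclusion.** The concern holds in a limited form. The only stated follow-up period ends at an outcome-dependent point and, if SAE collection follows it, deaths and serious complications after intubation go unrecorded. Truncation can only lower the SAE count. It lowers the per-patient rate used in section 9.6 unless intubation is counted as an SAE.

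The documents do not fix the size of the effect. What they support is a ceiling at each assumed rate on the patients affected (2 to 5 of the first 10, 4 to 10 of 20, if every failure is an intubation). The probabilities in the illustration rest on assumed event rates and show sensitivity, not an estimate. The primary result, the failure limit and the sample size stand.

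Severity: should fix, with medium confidence, because the undercount depends on two things the plan leaves open: the SAE collection window and the SAE definition.

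**What to change.** - Section 1, Duration: follow all treated patients for SAEs and vital status until hospital discharge or death, whether or not they are intubated. Keep intubation as the time-to-event endpoint in section 9.4.
- Section 8: define an SAE, give the collection window, and say whether intubation is itself an SAE.
- Section 9.6: say that SAEs in this window count in the SAE rate, and that the rate is the proportion of patients with at least one SAE, if that is what is meant.
- Section 9.4: add a descriptive report of in-hospital mortality and of SAEs after intubation, without a causal claim.

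The cost is a change of wording and some extra chart abstraction for a small number of inpatients at one centre. No visit, procedure or change in sample size is needed. The reported SAE rate may be higher than under the present wording, and the sponsor and DSMC should expect that when they read the 20% limit.

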3.1 Primary Objective

- Evaluate the incidence of intervention failure, defined as either requirement for endotracheal intubation or occurrence of excessive sedation (RASS ≤ -3).

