5.2 Exclusion Criteria

- Hypersensitivity to isoflurane or volatile anesthetics
- History of malignant hyperthermia
- Severe hepatic dysfunction
- Contraindications to NIV (e.g., facial trauma, uncontrolled secretions)
- GCS $<$ 12 or inability to protect airway
- Hemodynamic instability unresponsive to fluids
- Pregnancy or recent upper airway surgery/tracheostomy

6. Intervention

Isoflurane infusion will be initiated at 1.5 mL/h via syringe pump (Infusia SP7s®, Fresenius Kabi). The AnaConDa® device is placed between mask and ventilator Y-piece, with scavenging on expiratory limb. Fresh gas flow (FGF) is set at patient minute ventilation plus 0.5 L/min. Target $F_{et}\%$ (end-tidal concentration) is 0.3–0.5 vol% for light sedation. NIV settings:

- Pressure support: 8–20 cm H₂O (titrated to 10 mL/kg IBW)
- PEEP: 4–6 cm H₂O
- RR: 12–16 breaths/min (I:E 1:3–1:4)
- FiO_2 : 30–40% (titrate to SpO_2 88–94%)

Sedation depth will be adjusted based on RASS, targeting -1 to -2 . Excessive sedation ($\text{RASS} \leq -3$) prompts immediate cessation (failure event).

7. Study Assessments

Assessment	Baseline	2 h	6 h	12 h	24 h
Vital signs (HR, BP, RR)	✓	✓	✓	✓	✓
ABG parameters	✓	✓	✓	✓	✓
RASS	✓	✓	✓	✓	✓
VAS comfort score	✓	✓	✓	✓	✓
Intervention failure	—	✓	✓	✓	✓

8. Safety Monitoring

- Continuous pulse oximetry, ECG, non-invasive BP every 15 minutes for first hour, hourly thereafter.
- Monitor for hypotension ($\text{SBP} < 90 \text{ mmHg}$), bradycardia ($\text{HR} < 50 \text{ bpm}$), respiratory depression ($\text{RR} < 10 \text{ breaths/min}$).
- ABG review for hypercapnia or hypoxemia.
- Report serious adverse events (SAEs) within 24 hours to DSMC.

9. Statistical Analysis Plan

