9.2 Analysis Populations

- **Intent-to-Treat (ITT):** All enrolled patients who received any study intervention.
- **Per-Protocol (PP):** Patients completing at least 2 hours of sedation without major protocol violations.

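### A treated patient who dies with no documented need for intubation and no recorded RASS ≤ -3 is scored as a non-failure in the primary outcome

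*Combined protocol and SAP*

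**What the plan says.** - **Definition.** Section 3.1 has failure "defined as either requirement for endotracheal intubation or occurrence of excessive sedation (RASS ≤ -3"). The synopsis gives the same two components more briefly: "Incidence of intervention failure (intubation or excessive sedation"). Neither names death or a time window.
- **Analysis.** Section 9.3 takes the proportion of failures in the ITT set with a Wilson 95% interval. Section 9.2 defines that set as "All enrolled patients who received any study intervention". Section 9.5 deals with missing RASS and VAS only. No section says how a death is scored.
- **Timing.** The section 7 table schedules "Intervention failure" at 2, 6, 12 and 24 h. The synopsis gives the duration as "24 hours of sedation monitoring; follow-up until discharge or intubation".
- **Time to event.** Section 9.4 plans a Kaplan–Meier curve for time to intubation, with no rule for death.
- **Mortality elsewhere.** Section 2 says that "non-invasive ventilation (NIV) reduces intubation and mortality risks", but mortality is not an outcome anywhere in the plan.
- **Safety route.** Section 8: "Report serious adverse events (SAEs) within 24 hours to DSMC". Section 9.6 has the DSMC consider early termination after 10 patients if failure exceeds 50% or the SAE rate exceeds 20%.
- **Reference rate.** Section 9.1: "Assuming baseline NIV failure/intubation rate of 50"%, with a 30-point absolute reduction, 20 patients and 80% power.

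**The concern.** The primary outcome is meant to show how often the intervention goes wrong. Under 3.1, 9.2 and 9.3 together, a treated patient who dies without meeting either component adds one to the denominator and nothing to the numerator. The worst outcome on NIV then improves the primary result. The error runs in one direction only: it cannot raise the failure rate.

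The deaths at issue are those between scheduled assessments, those where intubation was not pursued and no need for it was documented, and, if the window runs past 24 h, those after RASS assessment has ended. With 20 patients, one or two of them move the estimate by 5 or 10 percentage points. The same count feeds the failure limb of the interim rule in 9.6.

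**Working it through.** **1. The plan's own figure.** From 9.1: reference p0 = 0.50, target p1 = 0.50 − 0.30 = 0.20, two-sided α = 0.05, power 80%. The one-sample formula gives

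n = [(1.960·√(0.5·0.5) + 0.842·√(0.2·0.8)) / 0.30]² = 19.26, rounded up to 20.

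An exact binomial check at n = 20 (5 or fewer failures) has power 0.804. The stated 20 reproduces and is not in dispute. The expected result under 9.1 is 20% of 20 = 4 failures.

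**2. What one or two patients do to the interval.** The Wilson interval has centre (p + z²/2n)/(1 + z²/n) and half-width z·√(p(1−p)/n + z²/4n²)/(1 + z²/n), with z = 1.960 and n = 20.

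| Failures | Rate | Wilson 95% CI |
|---|---|---|
| 4/20 | 20% | 8.1% to 41.6% |
| 5/20 | 25% | 11.2% to 46.9% |
| 6/20 | 30% | 14.5% to 51.9% |

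One reclassified patient at 5/20, or two at 4/20, bring 50% inside the interval.

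**3. How often that would happen.** The documents give no rate for uncounted deaths, so it is assumed. Let c be the true rate of the composite that includes death, and d the part of it made up of deaths meeting neither component. The number of counted failures X and of uncounted deaths Y are then trinomial with probabilities c − d, d and 1 − c. The table gives P(X ≤ 5 and X + Y ≥ 6) for n = 20.

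| Composite c | d = 1 point | d = 2 | d = 5 | d = 10 | Share of failures that d = 10 implies |
|---|---|---|---|---|---|
| 20% | 3.1% | 6.0% | 12.8% | 18.5% | 10/20 = one half |
| 30% | 3.9% | 7.9% | 20.1% | 38.8% | 10/30 = one third |
| 50% | 0.5% | 1.1% | 3.5% | 10.5% | 10/50 = one fifth |

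The last column shows how much the largest figures ask of the reader. The 10-point value is an assumption, not a bound.

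**4. The interim.** More than 50% of 10 means 6 or more. P(X ≤ 5 and X + Y ≥ 6) for n = 10, over d = 1 to 10 points, is 0.1% to 0.6% at c = 20%, 0.7% to 4.1% at 30% and 2.4% to 21.1% at 50%. These are chances of a changed failure count. The SAE limb of 9.6 is met by three deaths in 10 (30% > 20%) but not by two (20% is not above 20%). Leaving out cases with three or more uncounted deaths, the d = 10 values fall to 0.2%, 2.5% and 16.3%.

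**The case against.** The case on the other side has several parts.

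- **Most deaths would be caught already.** Patients are monitored continuously, RASS is scheduled to 24 h, and those with GCS < 12 or an unprotected airway are excluded. A deteriorating patient would plausibly meet a component before dying. This stands as a limit on size. It would be wrong to infer that every death is scored as a success.
- **Deaths are not hidden.** They go to the DSMC as SAEs, and 9.6 has a separate SAE limb. This also stands, so the documents do not support a reading that safety oversight misses deaths. The DSMC report does not correct the estimate in 9.3, however.
- **The 50% line decides nothing.** Section 9.3 plans an estimate and an interval, with no test. That is right, and step 2 of the working shows sensitivity at n = 20, not a reversed conclusion.
- **The synopsis and 9.4 are shorthand.** Section 3.1 gives the full definition, with need for intubation sufficient. The shorter wording elsewhere is best read as abbreviation. It should be aligned, but it is not a competing definition.
- **The window can be inferred.** The section 7 schedule points to 24 h, and follow-up to discharge can coexist with that. A reader might infer a contradiction, but there is none. What is missing is a statement of which window the primary proportion uses.

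None of this supplies a rule for the remaining deaths.

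**Conclusion.** The gap is certain on the text; its size is not known. As written, a treated patient whose death meets neither component is a non-failure, and the primary failure rate is biased downward by however many such patients there are.

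If they are 1 or 2 in 100, the chance that the count falls at 5/20 or fewer while the composite with death is 6/20 or more is 0.5% to 7.9% across composites of 20%, 30% and 50%. At 10 in 100 it is 10.5% to 38.8%, but only if one fifth to one half of all failures are such deaths, and nothing in the documents suggests that. The effect on the interim is small unless true failure is near 50%.

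This should be fixed because it bears on the meaning of the primary endpoint and is cheap to correct. It does not invalidate the sample size arithmetic or the safety reporting. The unstated window, the abbreviated wording and the absence of death from the end-of-follow-up statement are secondary clarifications.

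**What to change.** - In the synopsis, 3.1, 9.3 and 9.6, use one definition of failure: requirement for intubation, RASS ≤ -3, or death without prior intubation.
- State one window for the primary outcome. 24 h matches the section 7 schedule. Failure to discharge can then be a secondary or sensitivity analysis.
- Report each component separately, and all deaths separately. Name death in the end-of-follow-up statement.
- In 9.4, treat death as a competing event for time to intubation, or analyse time to intubation or death.

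**Cost.** The change is mainly to protocol and SAP text. Follow-up to discharge is already planned for patients who are not intubated, so no visits are added.

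There are two downsides. The observed failure rate may be higher. The 50% in 9.1 belongs to an undefined NIV failure/intubation endpoint whose death content is unknown, so any comparison with it must be restated for, or limited to, a matching endpoint and window. If the reference stayed at 50% while the true rate with death rose from 20% to 25% or 30%, the chance of 5/20 or fewer would fall from 0.80 to 0.62 or 0.42. The sample size statement should therefore be rechecked once the reference is matched.

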9.3 Primary Outcome Analysis

- Calculate proportion of intervention failures in ITT population.
- 95% confidence interval (CI) using Wilson's method.

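### Patients whose isoflurane or NIV is abandoned without intubation or RASS ≤ -3 count as non-failures, and no outcome in the plan reports them

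*Combined protocol and SAP*

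**What the plan says.** The synopsis gives the primary objective as "Incidence of intervention failure (intubation or excessive sedation"; Section 3.1 has the same two components, with failure "defined as either requirement for endotracheal intubation or occurrence of excessive sedation (RASS ≤ -3". Section 6 sets a RASS target of -1 to -2. The only stop of isoflurane that it labels is RASS ≤ -3, which "prompts immediate cessation (failure event".

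Section 9.2 defines ITT as every enrolled patient who received any of the intervention, and per-protocol as at least 2 hours of sedation without a major violation. The primary analysis in 9.3 is "Calculate proportion of intervention failures in ITT population", with a Wilson 95% interval. Section 9.4 summarises RASS and VAS at each time point against baseline; its categorical outcomes are intubation and excessive sedation.

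Section 2 states the purpose: "This pilot protocol aims to assess feasibility and safety of isoflurane sedation via AnaConDa® in AE-COPD on NIV". It gives as background that "NIV intolerance due to agitation or dyssynchrony often necessitates invasive ventilation, with attendant complications".

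No section says how to classify a stop of isoflurane or NIV for agitation, mask intolerance or an adverse effect. None mentions another sedative or an opioid. The schedule in Section 7 has no row for the time or reason of stopping, or for other sedatives.

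**The concern.** In a feasibility pilot, a basic question is how many patients could be kept on the intervention. Here a patient taken off isoflurane or NIV early, and managed without intubation, stays in the ITT denominator and adds nothing to the numerator. Too much sedation is a failure; too little sedation that leads to abandonment is not.

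The same patient affects the secondary results. RASS and VAS are still scheduled at 6, 12 and 24 h after a stop at, say, 3 h. Section 9.5 deals only with missing values, so values observed after the stop, or on another drug, are pooled with those obtained on isoflurane.

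The consequence is a report in which abandoned patients appear only as successes. Because the schedule does not provide for recording stops, a later analysis to separate them is not assured.

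**Working it through.** **1. Classification under the plan as written** (Sections 3.1, 6, 9.2, 9.4)

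| Course within 24 h | Primary (ITT) | Per-protocol | Counted in another outcome? |
|---|---|---|---|
| Intolerance, then intubation | Failure | Failure if at least 2 h of sedation | Yes (intubation) |
| RASS ≤ -3 | Failure | Failure if at least 2 h of sedation | Yes (excessive sedation) |
| Stopped before 2 h, neither event | Non-failure | Excluded | No |
| Stopped after 2 h, neither event | Non-failure | Non-failure, absent a major violation | No |

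The last two rows are the gap. They follow from the definitions whatever is done after the stop; use of another sedative is not needed for the argument.

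**2. The plan's own figure.** Inputs from 9.1: 50% reduced by 30 points to 20%, two-sided α = 0.05, power 80%. Read as one sample against a fixed 50%:

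n = [(1.96·√(0.5·0.5) + 0.842·√(0.2·0.8)) / 0.3]² = [(0.980 + 0.337) / 0.3]² ≈ 19.3, so 20.

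Exact binomial at n = 20: reject with 5 or fewer failures, lower-tail probability 0.0207 at 50%, power 0.804 at 20%. The sample size reproduces and is not in question.

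**3. Size per patient.** 1/20 = 5 percentage points.

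**4. Wilson intervals**, n = 20, z = 1.96:

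[p + z²/2n ± z·√(p(1−p)/n + z²/4n²)] / (1 + z²/n), with z²/2n = 0.0960, z²/4n² = 0.0024 and 1 + z²/n = 1.1921.

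- 5/20: (0.3460 ± 1.96·√(0.009375 + 0.002401)) / 1.1921 = 0.290 ± 0.178, or 11.2% to 46.9%.
- 6/20: (0.3960 ± 1.96·√(0.010500 + 0.002401)) / 1.1921 = 0.332 ± 0.187, or 14.5% to 51.9%.

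The documents give no rate of abandonment. As an assumed range, take 0 to 4 such patients on top of the 4/20 expected at the design rate of 20%:

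| Abandoned (assumed) | Failures if counted | Proportion | Wilson 95% CI |
|---|---|---|---|
| 0 | 4/20 | 20% | 8.1–41.6% |
| 1 | 5/20 | 25% | 11.2–46.9% |
| 2 | 6/20 | 30% | 14.5–51.9% |
| 3 | 7/20 | 35% | 18.1–56.7% |
| 4 | 8/20 | 40% | 21.9–61.3% |

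The upper limit passes 50% only between 5 and 6 failures. A single patient crosses that line only when exactly 5 are already counted, which at a true rate of 20% has probability 15504 · 0.2⁵ · 0.8¹⁵ = 0.175. From 4/20, two are needed.

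**The case against.** A reader might infer that the primary endpoint misses the very failure the trial sets out to treat. The documents do not support that. Section 2 presents intolerance as leading to invasive ventilation, and intubation is counted. Entry under 5.1 does not require agitation or NIV intolerance. What is missed is abandonment that does not end in intubation or RASS ≤ -3.

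A reader might also infer that the primary proportion is biased towards success. It estimates the endpoint as defined, and a broader endpoint is a design choice. Co-sedation is hypothetical, since the documents neither permit nor forbid it, and it could act either way: it might avert an intubation, or produce a RASS ≤ -3 that is then charged to isoflurane. The net direction is not known.

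The plan is not blind to under-sedation. RASS and VAS at fixed times may show a patient who is still agitated, and SAE reporting under Section 8 would bring a stop for a serious event to the DSMC. Neither counts stops, and the per-protocol set, which drops stops before 2 h, is assigned to no analysis in 9.3 or 9.4.

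There is also a sound case against widening the primary. The 50% in 9.1 is described as a rate of NIV failure or intubation and is not stated to cover drug discontinuation, so a wider composite set against it may not compare like with like. If the wider rate were 25% or 30%, the chance of showing it to be below 50% with 20 patients would be 61.7% or 41.6%, against 80.4% at 20%. The more-than-50% trigger in 9.6 also rests on the failure count, so a wider definition would alter an early-termination rule. These arguments stand and shape the fix; they do not remove the gap in recording and reporting.

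**Conclusion.** The point holds as a gap in classification, recording and reporting. By the plan's own definitions, a permanent stop of isoflurane or NIV without intubation or RASS ≤ -3 is a non-failure, no outcome counts it, and later RASS and VAS values are credited to isoflurane. That sits poorly with a stated aim of feasibility and safety.

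The size is 5 points per patient. The total is unknown because no discontinuation rate is given; the 0 to 4 patients used above are an assumption. It is tempting to say that one abandoned patient reverses the trial's conclusion, but that is true only at exactly 5/20. Moreover, 9.3 plans a proportion and an interval only; the comparison with 50% is inferred from 9.1.

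**What to change.** Keep the present primary endpoint and leave the 9.6 trigger on its existing definition. Then:

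- **Section 7 and the CRF:** record the time and reason isoflurane or NIV was stopped, and any concomitant sedative or opioid (drug, time, reason).
- **Sections 3.2 and 9.4:** add a secondary outcome, treatment failure including discontinuation: primary failure, or permanent stop of isoflurane or NIV within 24 h for intolerance, inadequate sedation or an adverse effect. Report it in the ITT population with a Wilson 95% interval. Report use of other sedatives descriptively.
- **Section 9.4:** flag RASS and VAS values taken after a stop or after another sedative, and repeat the summary without them.
- **Interpretation:** do not compare the wider composite with the 50% in 9.1 unless that reference is shown to cover the same events.

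The cost is a CRF line, some protocol and SAP wording, and one more reported proportion, which cannot be lower than the primary and may look less favourable. The sample size is unaffected because the primary does not change. No drug, dose or stopping rule is proposed; those remain with the investigator.
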